**All vaccines can be administered to persons with a minor illness such as diarrhea, mild upper respiratory infection without fever.*
16. A reported temperature greater than or equal to 100.4°F (38.0°C) within 72 hours prior enrollment or a temperature (measured by temporal artery thermometer) greater than or equal to 100.4°F (38.0°C) at the time of enrollment*
**This may result in a temporary delay of vaccination*
17. Receipt of an antipyretic medication (acetaminophen or ibuprofen) within 24 hours prior to enrollment*
**This may result in a temporary delay of vaccination*
18. Parent(s)/LAR is planning to administer a prophylactic antipyretic or medication on the day of, and/or within 7 days following Visit 1 or Visit 2*
**This exclusion does not apply if the caretaker indicates he/she might administer antipyretics or analgesics after vaccination to reduce fever or pain*
19. Long term (at least 14 consecutive days) oral corticosteroids (prednisone 2 mg/kg/day or equivalent other glucocorticoid), any parenteral steroids, high-dose inhaled steroids (>800 mcg/day of beclomethasone dipropionate or equivalent) or other immune-modifying drugs or immunosuppressants within the preceding 6 months prior to Visit 1*
**Topical and nasal steroids are allowed*
20. Any confirmed or suspected immunosuppressive or immunodeficient condition, based on medical history and or their provider's routine physical examination*
**No laboratory testing required*
21. Has an active neoplastic disease, a history of any hematologic malignancy, current bleeding disorder, or taking anticoagulants.
22. Unable to receive an intramuscular injection in the thigh*
** For example – a broken bone or cast for treatment of broken bone in a lower extremity, congenital anomaly in lower extremity precluding administration in the affected extremity or if deemed inappropriate by the study investigator*

23. Any condition deemed by the investigator to place the child at increased risk as a result of their participation in the study
24. Any child or grandchild of a study investigator or study team member

A modified list of Exclusion Criteria will be reviewed at Visit 2 to assess eligibility for continued study participation.

Subjects who meet any of the following exclusion criteria will not be eligible to continue participation in this study:

1. Has already completed influenza vaccination during the current season per ACIP recommendations

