5.5.2 Blinding

This study will be open label and study staff and subjects will not be blinded to treatment arm assignments.

Vaccine (Supply, Storage, and Administration) and Educational Materials

Vaccine Supply and Storage

For consistency, the same formulations of DTaP, IIV and PCV13 vaccines will be used throughout this study to the extent feasible. There are multiple products on the market for DTaP and IIV vaccines. In the United States, only one PCV13 product (Wyeth

Pharmaceuticals, Inc) is licensed (package inserts, available at <https://www.fda.gov/BiologicsBloodVaccines/Vaccines/ApprovedProducts/ucm093833.htm>)

Because Duke and Kaiser Study clinics may not stock the same DTaP and IIV products in their routine supply, DTaP and IIV (single dose vials or prefilled syringes) will be purchased for this study using contract Task Order funds. DTaP and IIV will be maintained either at the respective primary research center or their affiliated clinic sites in a monitored medication refrigerator at 2-8°C in accordance with package insert guidelines. Study supplied vaccines should be segregated from the clinic's routine vaccine supply. Study supplied vaccine may be transported between the primary research center and clinic sites using each site's Standard Operating Procedure for Study Product Transport as long as the cold chain is maintained.

- Infanrix® (GSK) will be purchased for use as the DTaP vaccine to be administered in this study. However, if there are vaccine supply issues at the time of the conduct of this study, Daptacel® (Sanofi) may be purchased and used in the place of Infanrix®.
- 2017-2018 Quadrivalent Fluzone® (Sanofi) will be purchased for use as the IIV administered in this study. If not available, an alternate US licensed IIV with an indication for this age group will be used.
- PCV13 (Wyeth) will be used as in this study. This is the only US FDA licensed PCV13 product available. Because both study sites routinely use the Wyeth PCV13 vaccine in their clinics, PCV13 will be supplied by the participant's clinic site from their usual vaccine supply for use in the study and will not be purchased using contract Task Order funds. PCV13 will be maintained at the respective clinic sites in a monitored medication refrigerator at 2-8°C in accordance with package insert guidelines and clinic standard operating procedures. The cost of PCV13 will be billed to patient's insurance.

Vaccine Administration

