Parent(s)/LAR(s) will record medical care utilization, use of antipyretic medications, and febrile seizure occurrence (**Table 3**) beginning on the evening of Visit 1 and Visit 2 (Day 1) and for the next 7 days following the study visits (through Day 8). On the evening of Visit 1 and Visit 2, medical care utilization related to fever, use of antipyretic medications, and febrile seizure occurrence should be rated from the time of Visit 1 or 2 until the information is recorded. For each subsequent day through Day 8, these factors should be assessed from the time the information is recorded on one day to the time information is recorded on the next day.

Table 3: Medical Care Utilization and Antipyretic Use		
	Yes	No
Did you give your child fever or pain medicine?	Yes	No
If yes, was it for fever?	Yes	No
If yes, was it for pain?	Yes	No
If yes, check type or types of medicine given		
 Acetaminophen (e.g. Tylenol)		
 Ibuprofen (e.g. Motrin, Advil)		
 Other		
Did your child receive medical attention?	Yes	No
If yes, was it related to fever?	Yes	No
	Yes	No
If yes, check type or types of attention received		
 Telephone call for medical advice		
 Medical office visit including urgent care visit		
 Emergency department visit		
 Hospital admission		
If yes, provide reason for medical attention		
Did your child have a seizure?	Yes	No
If yes, was it related to fever?	Yes	No

For this study, medical care utilization, antipyretic use and the occurrence of febrile seizures will be documented using either the electronic memory aid through REDCap or the paper memory aid. The preferred method for documentation in this study is REDCap. All parent(s)/LAR(s) will be encouraged to use the paper memory aid as a tool to initially record information and then enter information into REDCap; however, they can directly enter information into REDCap if desired without using paper. For parents electing to use REDCap, missing data will be verified with the parent(s)/LARS on day 9 as needed following Visits 1 and 2. Parents/LAR using the paper memory aid alone will submit the Visit 1 memory aid to study staff during Visit 2, and will mail the study Visit 2 memory aid to the study team following the 8-day post-visit 2 period. The study team will review the paper memory aid at the time of receipt.

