8 ANALYSIS OF STUDY OBJECTIVES

8.1 Primary Objective

The primary objective (PO 1) of the study is to compare the proportion of children with fever (temperature $\geq 38.0^{\circ}\text{C}$ or $\geq 100.4^{\circ}\text{F}$) on day 1 and/or day 2 following Visit 1 and/or Visit 2. This information is captured on the memory aid form which is captured in the REDCap database. Fever on day 1 and/or day 2 after either visit will be counted as positive (1) for this analysis and no fever reported will be negative (0). The proportions will be compared between the simultaneous versus the sequential group using a Mantel-Haenszel statistic in a stratified analysis by site to control for the randomization blocks at the two-sided alpha 0.05 level. The relative risk and corresponding 95% confidence interval for the occurrence fever will also be calculated.

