8.3 Exploratory Objectives

There are eight exploratory objectives for this study.

- a) The first exploratory objective (EO 1) is to compare the height and duration of fever on day 1 and/or day 2 after Visit 1 and Visit 2 (separately and combined) in the simultaneous versus sequential group. The average peak temperature of each child with fever during the risk window of days 1 and 2 (temperature $\geq 38.0^{\circ}\text{C}$ or $\geq 100.4^{\circ}\text{F}$) and the total number of fever degree-days (temperature $\geq 38.0^{\circ}\text{C}$ or $\geq 100.4^{\circ}\text{F}$) following Visit 1, Visit 2 and Visit 1 and 2 combined will be presented by simultaneous and sequential vaccination groups. These six comparisons will be made using a Mann-Whitney U/Wilcoxon rank-sum test.
- b) The second exploratory objective (EO 2) is to compare the use of antipyretics for fever on day 1 and/or day 2 after Visit 1 and Visit 2 (separately and combined) in the simultaneous versus sequential group. The use of antipyretics for fever on day 1 and/or day 2 after Visit 1 and Visit 2 (separately and combined) will be presented for the simultaneous versus sequential group in tables. These three proportions of children with antipyretic use on day 1 and/or day 2 following Visit 1, Visit 2, and Visit 1 and Visit 2 combined will be compared using a Mantel-Haenszal statistic in a stratified analysis by site between the simultaneous and sequential vaccination groups.
- c) The third exploratory objective (EO 3) is to describe and compare the level of severity of fever following Visit 1 and Visit 2 separately, in the simultaneous versus sequential group. Fever will also be assessed at different levels of severity (Grades 1, 2, and 3) on day 1 and/or day 2 and days 3-8 following Visit 1 and separately for Visit 2. The grade levels are defined in Table 2.

Temporal Artery Temperature	None	Mild (Grade 1)	Moderate (Grade 2)	Severe (Grade 3)
°C	≤ 37.9	$\geq 38.0 - \leq 38.5$	$\geq 38.6 - \leq 39.5$	≥ 39.6
°F	≤ 100.3	$\geq 100.4 - \leq 101.3$	$\geq 101.4 - \leq 103.1$	≥ 103.2

There will be six (day 1 and/or day 2, days 3-8, and days 1-8 following Visit 1 and separately for Visit 2) statistical comparisons performed at the alpha 0.05 level. These group comparisons will be made using a Mantel-Haenszel statistic (row mean scores difference with standardized midranks scores [modified ridit scores]) in a stratified analysis by site to control for the randomization blocks.

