9 SENSITIVITY ANALYSES

Sensitivity analyses will be performed under three conditions:

- to exclude those who received antipyretics on day 1 and/or day 2 following Visit 1 and/or Visit 2.
- to extend the risk window for fever to day 3 after Visit 1 and Visit 2.
- to compare the effect of the first versus second dose of current seasonal influenza vaccine

These sensitivity analyses will be performed for the primary objective in both study populations (ITT and Per Protocol). The statistical comparison will be made using a Mantel-Haenszel statistic in a stratified analysis by site to control for the randomization blocks. No adjustments will be made to the alpha level (two-sided $\alpha=0.05$) for these sensitivity analyses.

Appendix 1

Major Protocol Violations

Study Title: A Prospective, Randomized, Open-label Clinical Trial to Assess Fever Following Simultaneous versus Sequential Administration of 13-valent Conjugate Pneumococcal Vaccine, Diphtheria Toxoid, Tetanus Toxoid, and Acellular Pertussis Vaccine and Inactivated Influenza Vaccine in Young Children

Short Title: Fever after Simultaneous versus Sequential Vaccination in Young Children

Sponsor: Centers for Disease Control and Prevention Clinical Immunization Safety Assessment (CISA) Project

Lead Site Principal Investigator: [name], MPH

Contributing Site Principal Investigator: [name]

Centers for Disease Control and Prevention (CDC) Principal Investigator: [name]

CDC Sub-principal Investigator: [name]

NCT #: 03165981

Purpose: To define major protocol violations that will be used to establish the Per Protocol Population for the Fever after Simultaneous versus Sequential Vaccination in Young Children study

Background: Per the protocol analysis plan there will be two study populations, the Intent-to-Treat (ITT) and Per Protocol populations. The ITT Population includes any participant that was enrolled, randomized into the study, and received at least one study vaccine at Visit 1. The Per Protocol Population is a subset of the ITT Population excluding those participants who do not provide valid temperature data on days 1 and 2 following Visit 1 and Visit 2 and those with major protocol violations as determined by the study investigators. Statistical analyses will be performed for both study populations, or the ITT Population only if no participants are excluded from the Per Protocol Population.

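### The antipyretic sensitivity analysis drops children medicated during the endpoint's own window, so it discards recorded fevers and its relative risk can move either way

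*Combined protocol and SAP*

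**What the plan says.** SAP section 9 lists three sensitivity conditions for the primary objective, to be run in both the ITT and Per Protocol populations with the site-stratified Mantel-Haenszel statistic. The first is "to exclude those who received antipyretics on day 1 and/or day 2 following Visit 1 and/or Visit 2". Protocol 6.2.6 has the same rule. Neither text limits it by the reason for use, by whether a fever was recorded, or by whether the dose came before or after the reading.

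The primary endpoint covers the same days. SAP 8.1 states: "Fever on day 1 and/or day 2 after either visit will be counted as positive (1) for this analysis"; otherwise "no fever reported will be negative (0".

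Protocol 4.2, exclusion 18, bars planned prophylactic use, but its footnote says: "This exclusion does not apply if the caretaker indicates he/she might administer antipyretics or analgesics after vaccination to reduce fever or pain". The diary (protocol 5.7, Table 3) asks whether a medicine was given and then "If yes, was it for fever", with a parallel question for pain. Exploratory objective 2 (SAP 8.3) is to "compare the use of antipyretics for fever on day 1 and/or day 2 after Visit 1 and Visit 2". On blinding, protocol 5.5.2 says: "This study will be open label and study staff and subjects will not be blinded to treatment arm assignments".

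**The concern.** The exclusion conditions on something that happens after randomisation and is partly caused by the outcome. A child whose temperature reaches 38.0 °C and who is then treated is a recorded event in the primary analysis, yet is absent from this one. The children left are selected on fever status, and selected differently by arm if parents who know the assignment medicate differently.

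The plan does not state the purpose of the rule. The natural reading is that it guards against masking, where medication given early suppresses a fever that would otherwise have been recorded. Masking can only affect medicated children with no recorded fever, who are coded 0. Excluding a medicated child with a recorded fever resolves no uncertainty.

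What is at stake is how the check is read. Agreement or disagreement with the primary result could come from medicating behaviour alone.

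**Working it through.** **Inputs from the documents.** Fever 36% (simultaneous) v 18% (sequential), 126 per arm, two-sided alpha 0.05, 90% power (protocol 6.1, SAP 4.2). Planned sites 160 and 120 children (protocol 4.3).

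**Reproducing the plan's figure.** A two-proportion test with pooled null variance gives power 0.9006 at 126 per arm. A simulated site-stratified Mantel-Haenszel test also gives 0.90, with 72 and 54 children per arm (160 × 0.9 / 2 and 120 × 0.9 / 2). Expected fevers: 126 × 0.36 + 126 × 0.18 = 45.4 + 22.7 = 68.

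**Effect of the exclusion.** Let p be the fever proportion, f the medicated share of febrile children and g the medicated share of afebrile children. After exclusion the fever proportion is

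p(1−f) / [p(1−f) + (1−p)(1−g)].

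The odds of fever in an arm are thus multiplied by (1−f)/(1−g). The planned odds ratio is (0.36/0.64) / (0.18/0.82) = 2.56. If f and g are the same in both arms, the odds ratio is preserved, and with f > g the RR drifts up from 2.00 towards 2.56. If f differs by arm, the odds ratio itself changes: 70% v 50% multiplies it by 0.30/0.50 = 0.6.

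The documents give no values for f or g, so all values below are assumptions. Power is computed on the children retained.

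| Scenario (simultaneous v sequential) | f | g | Fever after exclusion | RR | Power |
|---|---|---|---|---|---|
| Equal use | 20% both | 10% | 33.3% v 16.3% | 2.04 | 84% |
| Equal use | 50% both | 10% | 23.8% v 10.9% | 2.19 | 68% |
| Equal use | 80% both | 10% | 11.1% v 4.7% | 2.39 | 37% |
| Unequal use | 70% v 50% | 20% | 17.4% v 12.1% | 1.44 | 17% |
| Unequal use | 60% v 50% | 20% | 22.0% v 12.1% | 1.82 | 42% |
| Unequal use | 50% v 60% | 20% | 26.0% v 9.9% | 2.63 | 81% |
| Unequal use | 50% v 70% | 20% | 26.0% v 7.6% | 3.42 | 91% |

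In the three equal-use rows, 54, 34 and 14 of the 68 fevers remain.

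**No true effect** (27% in both arms, g = 20%). Equal use gives RR 1.00. With f at 70% v 50%, RR is 0.65; at 50% v 70% it is 1.54. Each is rejected 22% of the time. With 60% v 50%, RR is 0.83 and rejection is 9%.

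The stratified simulation agreed: power 0.84, 0.69 and 0.37 for the equal-use rows, 0.17 and 0.92 for the two 20-point splits, and null rejection 0.22.

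**Keeping everyone instead** (f = 50%, g = 10%, both arms). The planned rule excludes about 52 children: 34 with a recorded fever and 18 without. Under the alternative only those 18 are undetermined: 126 × 0.64 × 0.1 ≈ 8 and 126 × 0.82 × 0.1 ≈ 10.

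| Coding of the 18 | Proportions | RR |
|---|---|---|
| All non-events | 36.0% v 18.0% | 2.00 |
| Imputed at the arm's own 36% / 18% | 38.3% v 19.5% | 1.97 |
| Imputed at 50% in both arms | 39.2% v 22.1% | 1.77 |
| All events | 42.4% v 26.2% | 1.62 |

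**The case against.** - **The stakes are limited.** This is one supporting analysis. The primary analysis keeps every medicated child, and no conclusion in the SAP formally turns on this result. That stands, and it caps the severity.
- **Downward bias needs unequal use.** With equal use by arm, and febrile children medicated more often than afebrile, the RR moves only upward, and a null effect stays null. If use is unrelated to fever and equal by arm, there is no bias at all. The large shifts need a 20-point gap between arms that the documents neither report nor size. This stands as a condition: open-label assignment makes a gap plausible, not certain. Power still falls with equal use.
- **The rule can work.** Suppose use is purely pre-emptive and unrelated to underlying fever, at 30% v 10%, and suppresses half of the fevers in users. The recorded RR is then (0.36 × 0.85) / (0.18 × 0.95) = 1.79, and exclusion restores 2.00. But if 60% of recorded fevers among the other children are also treated, it overshoots to 2.28. The entry footnote and exploratory objective 2 both anticipate treatment of fever.
- **The all-events coding is itself fragile.** With no true effect and 15% v 5% of afebrile children medicated, it gives RR 1.24 and 23% false rejection. Under the same assumption, with equal febrile use of 20% to 80%, the planned exclusion gives RR 1.09 to 1.11 and about 6%. That is why all-events coding should serve only as a bound.
- **Exploratory objective 2 would reveal unequal use for fever.** It would, but it does not correct this analysis or show how many excluded children had a recorded fever.

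**Conclusion.** The concern holds. As written, the exclusion discards recorded events whenever febrile children are medicated in the window, which the plan permits and expects. It also fails to isolate the only children masking could affect. Across the assumed rates tabulated, the RR runs from 1.44 to 3.42 around a planned 2.00, with power as low as 17%. Under no true effect, a 20-point difference in medicating febrile children gives 22% false rejection and a 10-point difference gives 9%.

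Movement below 2.00 and bias under the null depend on use that differs by arm. Loss of events and power needs only that febrile children are treated. The primary test and the sample size are untouched, so this is a change that should be made rather than one the trial depends on.

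**What to change.** Reword SAP section 9 and protocol 6.2.6 as follows.

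1. Keep all children. Count every recorded temperature of at least 38.0 °C on day 1 or 2 after either visit as an event, treated or not.
2. Treat as undetermined only children given an antipyretic in that window with no recorded fever in it. Rerun the site-stratified test and RR with them coded (i) as non-events, which is the primary coding; (ii) by imputation within arm and site over a pre-stated range of fever probabilities; and (iii) as events, as a bound.
3. Do not use antipyretic use as a predictor in the imputation. Every user with known status has a fever, so the model would impute only events.
4. Report the undetermined children by arm and by the Table 3 reason (fever or pain).
5. If the exclusion analysis is kept, label it descriptive and report the excluded children by arm and fever status. A composite of recorded fever or antipyretic given for fever may be added, but only as an extra version with its weakness stated.

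The cost is wording and a little extra analysis, because the diary already collects temperature, use and reason. The downside is that version (iii) and the composite count fevers perceived by parents. With 10% of afebrile children medicated in both arms (assumed), version (iii) dilutes RR 2.00 to 1.62 with 78% power, so it should not be the lead version.
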